3.14.3.8. Immunogenicity

3.14.3.8.1. Definitions of Sample Anti-drug Antibody Status

At a high level, an individual sample is potentially examined multiple times, in a hierarchical procedure, to produce a sample anti-drug antibodies (ADA) assay result and potentially multiple cross-reactive antibodies assay results and multiple neutralizing antibodies (NAb) assay results.

The cut points used, the drug tolerance of each assay, and the possible values of titers are operating characteristics of the assay. Figure GPID.3.2 details a flow chart that reflects the multitiered testing approach.

Abbreviations: ADA = antidrug antibodies; CP = cut point; GIPR = glucose-dependent insulinotropic polypeptide receptor; GLP-1R = glucagon-like peptide-1 receptor; LY = LY3298176 (tirzepatide); NAb = neutralizing antibodies; nGIP = native glucose-dependent insulinotropic polypeptide; nGLP-1 = native glucagon-like peptide-1; T2 = Tier 2; T4 = Tier 4.

Figure GPID.3.2. Flowchart of immunogenicity multitiered testing approach.

Table GPID.3.6 outlines results as reported from Tier 2a of the multitiered testing approach. Tier 4 results are reported similarly.

Table GPID.3.6. Sample ADA Assay Results

Sample Laboratory Result	Explanation	
Detected	ADA are Detected and Confirmed.	
Not Detected	The raw result as reported from the laboratory indicates Not Detected. The	
	clinical interpretation of such results depends on other factors	
	(see Table GPID.3.7).	
NO TEST, QNS, etc.	Sample exists but was unevaluable by the assay.	

Abbreviations: ADA = anti-drug antibodies; QNS = quantity not sufficient.

It may be the case that the presence of high concentrations of tirzepatide will affect ADA immunoassays, and conversely, that high levels of ADA may affect the measurement of tirzepatide concentrations. Thus, a tirzepatide drug concentration, assessed from a sample drawn at the same time as the ADA sample, plays a key role in the clinical interpretation of a sample when the laboratory results is Not Detected (see Table GPID.3.7).

Table GPID.3.7. Sample Clinical ADA Interpretation Results

Sample Clinical Interpretation	Explanation
ADA Present	ADA assay result is Detected.
ADA Not Present	ADA assay result is Not Detected, and simultaneous drug concentration is at a level that has been demonstrated to not interfere in the ADA detection method (that is, drug concentration is below the assay's drug tolerance level). For participants receiving placebo, drug concentration is not assessed and is assumed to be below the assay's drug tolerance level. If the drug concentration was planned but is not available for a treatment-period sample, a Not Detected sample will be declared ADA Not Present.
ADA Inconclusive	ADA assay result is Not Detected but the drug concentration in the sample is at a level that may cause interference in the ADA detection method.
ADA Missing	ADA sample not drawn, QNS, not tested, etc., causing there to be no laboratory result reported or the result is reported as "no test."

Abbreviations: ADA = antidrug antibodies; QNS = quantity not sufficient.

All ADA present samples will be evaluated for cross-reactive GIP (Tier 2b), cross-reactive GLP-1 (Tier 2c), NAb LY (tirzepatide) on GIP-R (Tier 4a), and NAb LY (tirzepatide) on GLP-1R (Tier 4b). If cross-reactive GIP is detected, NAb GIP on GIP-R (Tier 4c) is evaluated. If cross-reactive GLP-1 is detected, NAb GLP-1 on GLP-1R (Tier 4d) is evaluated (Figure GPID.3.2).

Similar terminology to Table GPID.3.8 applies for each type of cross-reactive and NAb assay. Importantly, each of these are distinct assays and, in general, have different assay operating characteristics.

The following are considered inconclusive for the NAb result:

- NAb LY on GIP-R: if the NAb result is not detected, and pharmacokinetic (PK) concentration is ≥ drug tolerance limit of the NAb LY on GIP-R assay
- NAb LY on GLP-1R: if the NAb result is not detected, and PK concentration is ≥ drug tolerance limit of the NAb LY on GLP-1R assay
- NAb GIP on GIP-R: if the NAb result is not detected, and PK concentration is ≥ drug tolerance limit of the NAb GIP on GIP-R assay
- NAb GLP-1 on GLP-1R: if the NAb result is not detected, and PK concentration is ≥ drug tolerance limit of the NAb GLP-1 on GLP-1R assay

To mitigate inconclusive cross-reactive NAb interpretations against native GIP and GLP-1 due to potential tirzepatide concentrations greater than or equal to the drug tolerance limit of the NAb GIP on GIP-R (Tier 4c) and NAb GLP-1 on GLP-1R (Tier 4d) assays, an *in silico* method utilizing results from Tiers 2b and 2c, Tiers 4a and 4b, and tirzepatide concentrations is introduced. The *in silico* method is outlined in Table GPID.3.8.

Table GPID.3.8. In Silico Classification for Cross-Reactive NAb

In Silico	Cross-Reactive		Circulating	In Silico Cross-
Classification	ADA Result	NAb Result	Tirzepatide Level (ng/mL)	Reactive NAb Interpretation
Cross-Reactive	Tier 2b: "Not	Tier 4a "Not Detected"	Any Value or Missing	Not Present
NAb to nGIP	Detected"	Or		
		Tier 4a: "Detected" or		
		N/A or Missing		
	Tier 2b: "Detected"	Tier 4a: "Not Detected"	< drug tolerance limit	Not Present
			of Tier 4a assay	
	Tier 2b: "Detected"	Tier 4a: "Not Detected"	≥ drug tolerance limit	Inconclusive
			of Tier 4a assay	
	Tier 2b: "Detected"	Tier 4a: "Detected"	< drug tolerance limit	Present
			of Tier 4a assay	
	Tier 2b: "Detected"	Tier 4a: "Detected"	≥ drug tolerance limit	Present
			of Tier 4a assay	
Cross-Reactive	Tier 2c: "Not	Tier 4b "Not Detected"	Any Value or Missing	Not Present
NAb to	Detected"	Or		
nGLP-1		Tier 4b: "Detected" or		
		N/A or Missing		
	Tier 2c: "Detected"	Tier 4b: "Not Detected"	< drug tolerance limit	Not Present
			of Tier 4b assay	
	Tier 2c: "Detected"	Tier 4b: "Not Detected"	≥ drug tolerance limit	Inconclusive
			of Tier 4b assay	
	Tier 2c: "Detected"	Tier 4b: "Detected"	< drug tolerance limit	Present
			of Tier 4b assay	
	Tier 2c: "Detected"	Tier 4b: "Detected"	≥ drug tolerance limit	Present
			of Tier 4b assay	

Abbreviations: ADA = antidrug antibodies; GIPR = glucose-dependent insulinotropic polypeptide receptor; GLP-1R = glucagon-like peptide-1 receptor; LY = tirzepatide; NAb = neutralizing antibody; nGIP = native glucose-dependent insulinotropic polypeptide; nGLP-1 = native glucagon-like peptide-1; Tier 2b = cross-reactive

ADA to nGIP; Tier 2c = cross-reactive ADA to nGLP-1; Tier 4a = NAb LY (tirzepatide) on GIPR; Tier 4b = NAb LY (tirzepatide) on GLP-1R.

Note: Only the drug tolerance limits of the Tier 4a and 4b assays are used for in silico classifications as they are lower than the drug tolerance limits of the Tier 2b and 2c assays, respectively.

3.14.3.8.2. Definitions of Immunogenicity Assessment Periods

Immunogenicity Baseline Observations: The baseline period for immunogenicity assessment for each participant includes all observations prior to the first dose of study treatment. In instances where multiple baseline observations are collected, the last nonmissing immunogenicity assessment prior to first administration of study drug is used to determine participant's ADA status and TE status (see below).

Immunogenicity Postbaseline Period Observations: Postbaseline period observations for each participant includes all observations after the first administration of study drug.

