8.5. Pharmacokinetics

Pharmacokinetic samples will be collected from all participants in this study.

Tirzepatide plasma concentrations will be determined from blood samples obtained from participants receiving tirzepatide treatment. Blood samples collected from participants assigned to the placebo arm will not be included in the bioanalysis of drug concentrations.

Blood samples for PK assessment will be collected prior to the dose administration and at the same time as the planned immunogenicity samples (that is, at Week 0 and then at Weeks 4, 12, 24, and 52 per the Study Schedule or additionally at follow-up and ET (reference SoA).

Samples will be analyzed at a laboratory approved by the sponsor and stored at a facility designated by the sponsor.

Concentrations of tirzepatide will be assayed using a validated liquid chromatography mass spectrometry method. Bioanalytical samples collected to measure tirzepatide concentrations will be retained for a maximum of 1 year following last participant visit for the study (Section 10.1.10). During this time, samples remaining after the bioanalyses may be used for exploratory analyses such as metabolism work, protein binding, and/or bioanalytical method cross-validation.

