Urine albumin, creatinine, UACR	
Hormones (female)	
Urine Pregnancy	Local laboratory
Serum Pregnancy	Assayed by Lilly-designated laboratory.

Clinical Laboratory Tests	Comments	
Follicle Stimulating Hormone (FSH)	Assayed by Lilly-designated laboratory.	
Pharmacokinetic Samples	 Assayed by Lilly-designated laboratory. Results will not be provided to the investigative sites. In the event of systemic drug hypersensitivity reactions (immediate or nonimmediate), additional blood samples will be collected including ADA, PK, and exploratory biomarker samples. PK samples for immunogenicity must be taken prior to drug administration. 	
Genetics sample	Assayed by Lilly-designated laboratory.	
Whole blood (EDTA)	Results will not be provided to the investigative sites.	
Exploratory Biomarker Samples	 Assayed by Lilly-designated laboratory. Results will not be provided to the investigative sites. 	
Serum	-	
EDTA Plasma		
P800 Plasma		
Immunogenicity Samples		
Anti-tirzepatide antibodies Anti-tirzepatide neutralizing antibodies	 Assayed by Lilly-designated laboratory. Results will not be provided to the investigative sites. In the event of systemic drug hypersensitivity reactions (immediate or nonimmediate), additional blood samples will be collected including ADA, PK, and exploratory biomarker samples. PK samples for immunogenicity must be taken prior to drug administration. 	

Abbreviations: ADA = antidrug antibody; CKD-EPI = Chronic Kidney Disease-Epidemiology Collaboration; EDTA = ethylenediaminetetraacetic acid; eGFR = estimated glomerular filtration rate; HDL-C = high-density lipoprotein cholesterol; LDL-C = low-density lipoprotein cholesterol; Lilly = Eli Lilly and company; PK = pharmacokinetic; UACR = urine albumin/creatinine ratio; VLDL-C = very low-density lipoprotein cholesterol.

10.3. Appendix 3: Adverse Events: Definitions and Procedures for Recording, Evaluating, Follow-up, and Reporting

The definitions and procedures detailed in this appendix are in accordance with ISO 14155.

Both the investigator and the sponsor will comply with all local medical device reporting requirements.

The detection and documentation procedures described in this protocol apply to all sponsor medical devices provided for use in the study. See Section 6.1.1 for the list of sponsor medical devices).

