10.5.1.7. Hypersensitivity Events

All allergic or hypersensitivity reactions will be reported by the investigator as either AEs, or if any serious criterion is met, as SAEs.

In the event of suspected drug hypersensitivity reactions (immediate or nonimmediate) in subjects who experience moderate-to-severe reactions as assessed by the investigator, unscheduled blood samples will be collected as outlined in Appendix 7 (Section 10.7).

Additional data, such as type of reaction and treatment received, will be collected on any AEs or SAEs that the investigator deems related to study drug via the eCRF created for this purpose.

Study drug should be temporarily interrupted in any individual suspected of having a severe or serious allergic reaction to study drug. Study drug may be restarted when/if it is safe to do so, in the opinion of the investigator.

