10.5.1.8. Injection Site Reactions

Injection site reactions will be collected on the eCRF separate from the hypersensitivity reaction eCRF. At the time of AE occurrence, samples will be collected for measurement of tirzepatide ADA and tirzepatide concentration.

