10.7. Appendix 7: Recommended Laboratory Testing for Hypersensitivity Events

Laboratory testing should be performed at the time of a systemic hypersensitivity event. The management of the AE may warrant lab testing beyond that described below and should be performed as clinically indicated. Laboratory assessments should be performed if the participant experiences generalized urticaria or if anaphylaxis is suspected.

- Collect the sample after the participant has been stabilized and within 1 to 2 hours of the event; however, samples may be obtained as late as 12 hours after the event as analytes can remain altered for an extended period of time. Record the time at which the sample was collected.
- Obtain a follow-up sample at the next regularly scheduled visit or after approximately 4 weeks, whichever is later.

Clinical Laboratory Tests for Hypersensitivity Events

Hypersensitivity Tests	Notes Selected test may be obtained in the event of anaphylaxis or systemic allergic/hypersensitivity reactions.	
Tirzepatide antidrug antibodies (immunogenicity/ADA)	Assayed by Lilly-designated laboratory. Results will not be provided to the investigative sites.	
Tirzepatide concentrations (PK)	Assayed by Lilly-designated laboratory. Results will not be provided to the investigative sites.	
Tryptase	Assayed by Lilly-designated laboratory. Results will not be provided to the investigative sites. Urine N-methylhistamine testing is performed in addition to tryptase testing. Collect the first void urine sample following the event. Collect a follow-up urine sample after approximately 4 weeks. Note: If a tryptase sample is obtained more than 2 hours after the event (that is, within 2-12 hours), or is not obtained because more than 12 hours have lapsed since the event, collect a urine sample for N-methylhistamine testing.	
N-methylhistamine	Will be performed if validated assay is available. Assayed by Lilly-designated laboratory. Results will not be provided to the investigative sites.	
Drug-specific IgE	Will be performed if a validated assay is available. Assayed by Lilly-designated laboratory. Results will not be provided to the investigative sites.	

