3.14.3.8.3. Definitions of Participant ADA Status

Treatment-emergent ADA (TE ADA)-evaluable participants: A participant with a nonmissing baseline ADA result and at least 1 nonmissing postbaseline ADA result.

TE ADA-unevaluable participant: any participant who does not meet the evaluable criteria.

Baseline ADA Present (preexisting antibody): ADA detected in a sample collected up to the first dose date and time.

Baseline ADA Not Present: ADA is not detected, and the corresponding PK concentration is missing or below the drug tolerance limit in a sample collected up to the first dose date and time.

TE ADA positive (TE ADA+) participant: an evaluable participant who had a:

- baseline status of ADA Not Present and at least 1 postbaseline status of ADA Present with titer ≥2× minimum required dilution (MRD), where the MRD is the minimum required dilution of the ADA assay, or
- baseline and postbaseline status of ADA Present, with the postbaseline titer being 2 dilutions (4-fold) greater than the baseline titer. That is, the participant has a baseline (B) status of ADA Present, with titer 1:B, and at least 1 postbaseline (P) status of ADA Present, with titer 1:P, with P/B ≥4.

As shown in Figure GPID.3.2, a titer is expected when the ADA assay result is Detected. On the occasion when the corresponding assay cannot be performed, in which case a titer value will be imputed for the purpose of TE ADA determination. A baseline sample with detected ADA and no titer is imputed to be the MRD (1:10), and a postbaseline sample with ADA detected and no titer is imputed to be one dilution above the MRD (1:20).

TE ADA-Inconclusive participant: a TE ADA-evaluable participant is TE ADA Inconclusive if ≥20% of the participant's postbaseline samples, drawn predose, are ADA Inconclusive and all remaining postbaseline samples are ADA Not Present.

TE ADA-negative (TE ADA-) participant: a TE ADA-evaluable participant is TE ADA- when the participant is not TE ADA+ and not TE ADA Inconclusive.

For each NAb assay, the following are defined:

NAb positive (NAb+) participant: a participant who is TE ADA+ and has a NAb positive sample in the postbaseline period.

NAb Inconclusive participant: a participant who is TE ADA+, is not NAb+, and all samples that have TE ADA+ titer have a NAb Inconclusive sample result.

NAb negative (NAb-) participant: a participant is neither NAb+ nor NAb Inconclusive.

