3.14.3.8.4. Analyses to be Performed

The count and proportion of participants who are TE ADA+ will be tabulated by treatment group, where the proportion is relative to the number of TE ADA-evaluable participants, as defined above. The tabulation will include the count and proportion of participants with ADA Present at baseline, and the count and proportion of TE ADA+ participants exhibiting each type of cross-reactive antibodies and NAb. This analysis will be performed for the planned treatment period.

The cross-reactive NAb will exclude Tier 4c and 4d results but include the *in silico* classification as cross-reactive NAb for summary.

A summary will be provided of the count and percentage of tirzepatide-treated participants experiencing specific TEAE (see Table GPID.3.9) by participant TE ADA status (TE ADA+, TE ADA-, TE ADA Inconclusive). The PT will be ordered by decreasing incidence in TE ADA+ status group.

Table GPID.3.9. Adverse Events for Analysis with Immunogenicity Results

TEAE category	Criteria		
Hypersensitivity reactions	Anaphylactic reaction SMQ (narrow or algorithm)		
	Hypersensitivity SMQ (narrow)		
	Angioedema SMQ (narrow)		
	Severe Cutaneous Adverse Reaction SMQ (narrow)		
	Vasculitis SMQ (narrow)		
Injection site reactions	Injection site reaction HLT		
	Infusion site reaction HLT		
	Administration site reaction HLT		

Abbreviations: HLT = high-level term; MedDRA = Medical Dictionary for Regulatory Activity; SMQ = standardized MedDRA query; TEAE = treatment-emergent adverse event.

Additional immunogenicity analyses as determined later may be presented. The relationship between antibody titers, PK parameters, and the pharmacodynamic response to tirzepatide may also be assessed.

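### Antibody samples triggered by injection site and hypersensitivity reactions count toward TE ADA+, so the planned table of those reactions by antibody status leans toward an association

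*SAP*

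**What the plan says.** **What triggers a sample.** Protocol 10.5.1.8, on injection site reactions, says "At the time of AE occurrence, samples will be collected for measurement of tirzepatide ADA and tirzepatide concentration" and sets no severity threshold. For suspected drug hypersensitivity that the investigator rates moderate to severe, Protocol 10.5.1.7 says "unscheduled blood samples will be collected as outlined in Appendix 7 (Section 10.7"). Appendix 2 (Protocol 10.2) says that for systemic drug hypersensitivity "additional blood samples will be collected including ADA, PK, and exploratory biomarker samples". Appendix 7 (Protocol 10.7) adds a second draw: "Obtain a follow-up sample at the next regularly scheduled visit or after approximately 4 weeks, whichever is later".

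**What is scheduled.** Protocol 8.5 places the PK samples, drawn together with the immunogenicity samples, "at Week 0 and then at Weeks 4, 12, 24, and 52 per the Study Schedule". The Schedule of Activities adds immunogenicity samples at EVd, early termination and Visit 99.

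**What counts.** SAP 3.14.3.8.2: "Postbaseline period observations for each participant includes all observations after the first administration of study drug". Under SAP 3.14.3.8.3 the treatment-induced route to TE ADA+ is "baseline status of ADA Not Present and at least 1 postbaseline status of ADA Present with titer" at or above twice the minimum required dilution. The treatment-boosted route also needs only one qualifying sample.

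**What is tabulated.** SAP 3.14.3.8.4 plans the count and percentage of tirzepatide-treated participants "experiencing specific TEAE (see Table GPID.3.9) by participant TE ADA status (TE ADA+, TE ADA-, TE ADA Inconclusive"). Table GPID.3.9 fills that category with hypersensitivity reactions (five SMQs) and injection site reactions (three high-level terms).

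**The concern.** The number of samples behind the classification depends on the outcome being classified. A participant who reacts is sampled more often because of the reaction. An extra sample can move someone into TE ADA+ but can never move them out, so the direction of the distortion is fixed.

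Order is ignored as well. Nothing requires the antibody to be detected before the reaction, so a reaction that precedes the first positive sample is still counted under TE ADA+.

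This is the display the SAP specifies for judging whether antibodies accompany these reactions. A modest excess of reactions among TE ADA+ participants could be real or could come from the sampling, and the table gives no means of telling which.

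**Working it through.** **1. Does another rule prevent it?** No.
- SAP Table GPID.3.2 says which scheduled and unscheduled measurements count for laboratory values and vital signs, but its footnote sends immunogenicity to Section 3.14.3.8.
- That section has no limit to scheduled samples. Its only sample restriction, to predose draws, belongs to the TE ADA-Inconclusive rule.
- The reference in 3.14.3.8.4 to the planned treatment period limits time, not type of sample, and is attached to the incidence tabulation.

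**2. How well do triggers and table rows match?** Injection site reactions match closely, since any severity triggers a sample and the table counts them all. Hypersensitivity matches only in part: the trigger is moderate-to-severe or systemic reactions, while the table counts every narrow SMQ term, including mild events. The Appendix 7 follow-up draw may also fall on a regular visit and add nothing.

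**3. Size.** The plan gives no figure to reproduce, so I used a model with no true link between antibodies and reactions.
- From the documents: about 350 participants on tirzepatide; four scheduled postbaseline samples to Week 52, and about four to six once later visits are included. I show K = 5.
- Assumed, because the documents are silent: per-sample positivity p, within-person correlation r between samples, a reaction rate e of 5%, and m extra samples per reactor.

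With a beta-binomial model, s = (1 − r)/r and b = (1 − p)s,

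P(no positive in n) = product over i = 0 to n − 1 of (b + i)/(s + i), or (1 − p)^n when r = 0.

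Let q0 = 1 − P(no positive in K) for non-reactors and q1 = 1 − P(no positive in K + m) for reactors. Bayes' rule gives

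P(reaction | TE ADA+) = e·q1 / [e·q1 + (1 − e)·q0]

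P(reaction | TE ADA−) = e(1 − q1) / [e(1 − q1) + (1 − e)(1 − q0)].

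Worked case, p = 0.20 and r = 0.3: the chance of at least one positive is 0.481 with 5 samples, 0.514 with 6 and 0.541 with 7.
- m = 1: 0.0532 / 0.0470 = 1.13.
- m = 2: 0.0559 / 0.0445 = 1.26.

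Spurious risk ratio, K = 5, e = 5%:

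| Positivity | Correlation | m = 1 | m = 2 | m = 4 |
|---|---|---|---|---|
| 10% | 0 | 1.26 | 1.54 | 2.19 |
| 10% | 0.3 | 1.11 | 1.22 | 1.40 |
| 20% | 0.3 | 1.13 | 1.26 | 1.48 |
| 30% | 0.3 | 1.16 | 1.30 | 1.59 |
| 30% | 0.6 | 1.07 | 1.13 | 1.24 |
| 10–30% | 0.9 | 1.02 | 1.03 | 1.06 |

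Over 4 to 6 scheduled samples, 1 to 4 extra, positivity 5–30% and correlation 0–0.9, the range is 1.01 to 4.9. The top needs independent samples at 30% positivity and four extra draws.

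**4. In people.** For the worked case, 350 × 5% = 17.5 reactors. One extra sample reclassifies 17.5 × 0.033 = 0.6 of them, and two reclassify 17.5 × 0.060 = 1.1. At a 10% reaction rate (35 reactors) the figures are 1.2 and 2.1.

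**5. Illustrative test.** The SAP plans none. In simulation (350 participants, 4,000 runs per scenario) a nominal two-sided 5% test rejected in 5.5–8.5% of runs with one or two extra samples. With four extra it rejected in 21% (20% positivity, correlation 0.3, 10% reaction rate).

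**6. Scheduled samples only.** Then m = 0, q1 = q0 and the expected ratio is 1.00. Simulated rejection was 4.7–5.3% in all seven scenarios.

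**The case against.** The strongest reply is that the effect is small and the obvious remedy has a cost of its own.

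- **Descriptive table.** Counts and percentages are planned, with no test or decision rule, and the distortion may amount to one or two people. This stands, and it limits the severity.
- **Assumed size.** Positivity, persistence and reaction frequency are not in the documents. If antibodies persist, scheduled samples already find them and the ratio is close to 1. This stands.
- **Samples not interchangeable.** Scheduled samples are predose where possible, whereas a reaction sample may be taken when drug levels are higher. SAP 3.14.3.8.1 says high tirzepatide concentrations may affect the antibody assay. Withdrawal after a reaction would also remove scheduled samples. Both could shrink the effect, and the model ignores both, as it ignores the Inconclusive category.
- **Loss of information.** Using scheduled samples alone would discard the draw taken at the reaction, which may be the one that shows a transient antibody. This is a sound argument against replacing the table, but not against showing both versions.
- **Existing mitigation.** Severe or serious reactions are events of special interest for which participant-level displays may be produced (SAP 3.14.3), and 3.14.3.8.4 allows further immunogenicity analyses. Both are optional, and neither commits to separating event-triggered samples.

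A reader might infer that the table will show an association whatever the truth, or that any excess among TE ADA+ participants is an artefact. The documents support neither reading. They establish a direction; in many plausible settings the expected shift is too small to be visible.

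**Conclusion.** The point holds as a minor one. As defined, the reaction-by-antibody-status summary is expected to lean toward an association when there is none, clearly for injection site reactions and partially for hypersensitivity.

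The direction follows from the text alone. The size rests on the assumed inputs: about 1.02 if antibodies persist, about 1.1 to 1.3 with one or two extra samples and partly persistent antibodies, and larger only with transient antibodies or recurrent reactions.

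Two further inferences would go too far. The table is not the only check possible, since the SAP leaves room for more; it is the only one specified. And no primary or key secondary result depends on it.

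**What to change.** In SAP 3.14.3.8.4:

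1. Present the Table GPID.3.9 summary twice: once with TE ADA status derived only from samples scheduled in the Schedule of Activities, and once with all samples.
2. List participants who are TE ADA+ only on an event-triggered sample.
3. Show the timing of each reaction relative to the participant's first TE ADA+ sample.
4. Keep all samples for the overall TE ADA incidence.

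The cost is SAP wording, one extra table, a short listing with timing, and two sets of TE ADA counts that need clear labels. No new samples are needed. The scheduled-only version may miss transient antibodies seen only at the reaction, which is why both versions should be shown.
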